One of the headline results from NAP5 was the disproportionately high incidence of AAGA for obstetric patients undergoing LSCS (~1:670 versus ~1:19,000 overall). General anaesthetics for obstetric patients recurrently typify many of the risk factors for AAGA identified by NAP5 and previous studies: rapid sequence induction, neuromuscular blockade, difficult airway management, obesity and frequent performance out-of-hours by non-consultant grade anaesthetists. This combination of factors is particular, if not unique, to obstetric anaesthetic practice and mandates classification of the subspecialty as high risk for AAGA. Furthermore, in n = 3/14 (21%) of cases of obstetric AAGA identified by NAP5, new significant psychological morbidity was reported. In one case the patient indicated a decision to litigate, which may also indicate further psychological harm.

The James Lind Alliance Anaesthesia and Perioperative Care Priority Setting Partnership identified the following question as being one of the top ten most important research topics in anaesthesia: “What long-term harm may result from anaesthesia, particularly following repeated anaesthetics?” [JLA PSP]. As the highest risk subgroup for one of the most important causes of harm following anaesthesia, obstetric anaesthetic practice warrants further research into AAGA. More explicitly, NAP5 set specific research implications for obstetrics, suggesting that further research was needed to “...define the incidence of AAGA as identified by the Brice questionnaire” [Research Implication 16.6, NAP5] and “to explore whether factors make obstetric patients more likely to report episodes of AAGA than the non-obstetric population” [Research Implication 16.7, NAP5].

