The Brice questionnaire [Brice 1970] has been used as a common standard in awareness research. Although minor variations have been applied [Avidan 2009], all retain the same five questions on recall of any events between induction of anaesthesia and emergence. Importantly, direct and systematic questioning is applied when using Brice questionnaires, which contrast with spontaneously patient reporting of AAGA in NAP5. This difference in methodology may partly account for the apparent divergence between the proportion of AAGA consistently reported in the overall surgical population with Brice questioning (~1:660) versus that by NAP5 (~1:19,000 overall). Although few studies have compared methods of AAGA testing, the Brice questionnaire is known to detect more cases of AAGA than unstructured direct questioning [Mashour 2013, Mashour 2009], and timing/repetition of Brice questioning may also influence the output [Mashour 2013, Sandin 2007, Davidson 2005, Leslie 2007]. These limitations, coupled with the debated gulf between incidence of AAGA established by Brice responses alone versus spontaneously reported incidence, mean that Brice has been regarded by some as not the “gold standard” methodology it is frequently implied to be [Cook 2015]. However, where Brice is uniquely important is as a common tool for comparison and as a screening method to identify a subpopulation that may be at need of further investigation.

Brice questionnaires have been applied only once before in obstetric patients [Paech 2009]. This observation study was primarily designed to investigate difficult airways in obstetric patients receiving a GA, but Brice questionnaires were also offered up to day two following surgery. A total 763 of 1095 obstetric patients were provided Brice questionnaires, of whom five cases were “Brice positive”, yielding an estimate of AAGA incidence of ~1:152. Of these, two were classed as “definite” and three as possible awareness. This preliminary study indicates that Brice positivity may indeed be much higher than it is in the general population. However, the lack of follow up beyond 48 hours, the wide confidence intervals and the fact that AAGA was not the study’s primary outcome make these results somewhat difficult to interpret.

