The most complete approach to investigating AAGA would be to screen all eligible individuals with a standardised tool, then rigorously assess each potential report with further investigation, before reaching a consensus classification of the event against pre-established definitions of AAGA. This is exactly the methodology to be adopted by our DREAMY study, using Brice questionnaire as the screening tool, but adding structured follow up, where appropriate, to elucidate the nature of the possible AAGA experience and its consequences. By taking this approach the research team aim to produce the most comprehensive analysis of AAGA in obstetric patients to date.

5 Research Question

The DREAMY study aims to fulfil research implications 16.6 and 16.7 from the National Audit Project 5 (NAP5) Report, in relation to AAGA in the obstetric population. These implications are to “...define the incidence of AAGA as identified by the Brice questionnaire” [Research Implication 16.6, NAP5] and “to explore whether factors make obstetric patients more likely to report episodes of AAGA than the non-obstetric population” [Research Implication 16.7, NAP5].

There are three competing research hypotheses: that the incidence of Brice positivity in obstetrics is similar to that of the general population (~1:660), similar to Paech’s [Paech 2009] already reported incidence (~1:152) or that the ratio between “Brice positive” and spontaneous reporting is maintained with the general population (~1:19).

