12.2 Statistical analysis plan

12.2.1 Estimated sample size and expected recruitment

Aggregation of NHS hospital-level audit data collected by PLAN and data for Greater London from the Office for National Statistics [ONS 2014] and Health & Social Care Information Centre [HSCIC 2014] confirms an annual expected birth rate of approximately 150,000 per annum across the maternity units in the Greater London area. Direct data, collected by PLAN from these units, covering 209,982 deliveries indicates that 4,027 GAs were provided to facilitate maternal delivery over the same time period; this is equivalent to a GA proportion of 1.92% (95% CI 1.86% – 1.98%) for all deliveries.

Given the expected annual birth rate of approximately 150,000, we therefore expect approximately 2,880 GA deliveries (95% CI 2,685 – 3,075) over a given 12 month data collection period. Patients undergoing non-LSCS obstetric surgery under GA (e.g. manual removal of placenta) will also be eligible for inclusion: based upon the same audit data this is expected to increase the total number of eligible patients by a factor of 1.12 to 3,225 (95% CI 3008 – 3444) per annum.

We aim to recruit at least 70% of all eligible patients – equivalent to a point estimate of ~2250 included participants over 12 months. Some women will be ineligible to participate due to the inclusion criteria (e.g. must be English speaking). We also expect a proportion of eligible women to decline involvement and the total number of recruitment hospital sites to vary, hence the final included number of participants may be lower or higher than this point estimate.

This is a descriptive observational study with the intent of capturing data from as many eligible participants over a 12 month study period as possible. The power of the expected sample size to exclude the possibility of not detecting an incidence of “Brice positive” AAGA that is at least three times the incidence described in the overall surgical patient population (taken as 0.15% or 1:660 [Sandin 2000]) using an exact binomial test and one-sided α of 0.05 is 88%.

Analysis and post hoc power calculations will be taken at the 12 month threshold, with a view to potentially extending the study dependent upon the confidence interval width of the identified AAGA proportion and ability to make a statistically significant comparison between previously documented incidences for AAGA.

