No formal estimate is made for the sample size of the baseline comparator group of non-AAGA patients who will be undergoing PTSD screening at 30 days. A lack of clear evidence regarding PTSD prevalence in patients receiving general anaesthesia for obstetric surgery would make such estimations speculative. Therefore, sample size has been preferentially determined by operational issues and consideration of sample size of studies identified in a previous systematic review of post-natal PTSD [Anderson 2012].

12.2.2 *Primary endpoint analysis*

The proportion of obstetric GA patients reporting AAGA will be expressed using binomial confidence intervals and compared with established values (see above for rectification of sample size).

There are three competing hypotheses. First, that the event proportion of Brice positivity in obstetrics is similar to that of the general population (i.e. ~1:660). If so, then we expect ~4 patients (binomial 95% CI 1 – 10). Second, that our incidence of Brice positivity will be similar to Paech’s already reported incidence (i.e. ~1:152 [Paech 2008]). Then we expect ~15 (95% CI 8 – 25) patients. Third, that the ratio between “Brice positive” and spontaneous reporting as in the general population (i.e. 1:660 vs 1:19,000) is maintained for obstetric patients (i.e. ~1:19). Then we expect 118 patients (95% CI 98 – 141). These figures for each of the three possible outcomes will be compared using Fisher’s exact test or chi-squared testing to yield a definitive answer as to which is the most likely hypothesis of the three.

Because we are administering the Brice questionnaire during 0-24h following the index GA (i.e. as soon as possible after GA recovery), we expect to obscure those cases who may otherwise report spontaneously. In other words, we do not expect by our methods to detect spontaneous reporting as such, as the questions will already have been asked. It is possible that some few patients may telephone in after their discharge to report that they now recall AAGA, perhaps triggered by the study, but even that would not fulfil the criterion for spontaneous reporting. We plan to class any such cases as “triggered reporting” and analyse them separately.

Subgroup analysis of the AAGA proportion will be conducted for type and urgency of surgical procedure (including emergency LSCS), de novo conversion from regional anaesthesia to GA and for GA inductions using propofol vs. thiopental.

12.2.3 *Secondary endpoint analysis*

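### The third hypothesis (~1:19, 118 expected cases) does not follow from the protocol's own rates, which give about 1:23 and 97 cases

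*Protocol*

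**What the plan says.** Section 4 (Background) gives the spontaneous-report incidence from the national audit "for obstetric patients undergoing LSCS (~1:670 versus ~1:19,000 overall"). It also contrasts the general surgical incidence "with Brice questioning (~1:660) versus that by NAP5 (~1:19,000 overall").

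Section 5 (Research Question) lists three competing hypotheses. In the third, the relation between Brice-positive and "spontaneous reporting is maintained with the general population (~1:19").

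Section 12.2.2 repeats this with its inputs, 1:660 against 1:19,000, and turns it into a count: the ratio "is maintained for obstetric patients (i.e. ~1:19). Then we expect 118 patients (95% CI 98 – 141"). For the first hypothesis (1:660) it says "If so, then we expect ~4 patients (binomial 95% CI 1 – 10"). For the second (1:152) it gives about 15, with 8–25. It then says that the figures for the three outcomes will be compared by Fisher's exact or chi-squared testing to settle which hypothesis is most likely.

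The counts rest on the planned sample in section 12.2.1, "equivalent to a point estimate of ~2250 included participants over 12 months".

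**The concern.** The third hypothesis is defined by a calculation, and the protocol supplies every input to it. Carried out, the calculation does not give the stated incidence. The figure is one of three reference values named for the primary comparison, and it appears in two sections.

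If ratio preservation is true at the rate the inputs imply, the most likely count is about 97, one below the lower end of the interval printed for that hypothesis.

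There is also a question of what the intervals represent. The text presents them as what to expect if a hypothesis is true, but they are confidence limits around a count treated as observed. For the rare-event benchmark the two differ visibly.

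**Working it through.** **Inputs**
- N = 2250 (section 12.2.1)
- General population: Brice-positive 1:660, spontaneous 1:19,000 (sections 4 and 12.2.2)
- Obstetric spontaneous rate: ~1:670, for LSCS (section 4), the only such rate in the protocol

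**Reproducing the printed figures**
- 2250/19 = 118.4, so 118 does follow from 1:19.
- Exact (Clopper-Pearson) 95% limits, multiplied by 2250, are 1.09–10.2 around 4, 8.4–24.7 around 15, and 98.1–140.6 around 118. After rounding these are the printed 1–10, 8–25 and 98–141.

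**Deriving the third hypothesis**
- Ratio = 19,000/660 = 28.79
- Incidence = 28.79 × (1/670) = 4.30%, or 1 in 670/28.79 = 23.3
- Expected count = 2250/23.27 = 96.7
- Binomial 2.5% and 97.5% quantiles at this incidence: 78 and 116
- Overstatement: 118/96.7 = 1.22

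**Can rounding explain the gap?** Let the three rates vary over 1:665–675, 1:655–665 and 1:18,500–19,500.
- Lowest denominator: 665 × 655/19,500 = 22.3, about 101 cases
- Highest denominator: 675 × 665/18,500 = 24.3, about 93 cases

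So rounding does not reach 1:19. That figure needs an obstetric spontaneous rate of 1 in 19 × 28.79 = 547, or a ratio of 670/19 = 35.3. The protocol contains neither.

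**Counts expected under each hypothesis** (binomial, N = 2250)

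| Hypothesis | Expected | 95% range of count | Printed |
|---|---|---|---|
| 1:660 | 3.4 | 0–7 | ~4 (1–10) |
| 1:152 | 14.8 | 8–23 | ~15 (8–25) |
| 1:23.3 (derived) | 96.7 | 78–116 | none |
| 1:19 (as stated) | 118.4 | 98–140 | 118 (98–141) |

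Under 1:660 the chance of 8 or more cases is 2.3%. The printed ranges for the first two hypotheses overlap at 8–10; the ranges under the hypotheses do not. Under 1:23.3 the chance of 97 or fewer cases is 54%, so the count would fall below the printed 98–141 more often than not.

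**The case against.** **The source rate is not stated.** Section 12.2.2 does not say that 1:670 was the rate used, and that rate is for LSCS, while the study also enrols women having other obstetric surgery. This stands as a limit on the correction: 1:23 assumes that 1:670 was meant. It does not rescue 1:19, because no other rate is given. Case mix is also a strained explanation. Section 12.2.1 expects non-LSCS surgery to multiply the eligible number by 1.12, so it makes up 0.12/1.12 = 10.7% of the total. To bring the overall rate to 1:547, that group would need a spontaneous rate of (1/547 − 0.893/670)/0.107, about 1:216. Nothing in the protocol supports that.

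**The intervals are not miscalculated.** A reader might infer that the 1–10 for the first hypothesis is an arithmetic error. It is not: all three intervals carry a confidence-interval label and are the exact limits for their counts. What remains is that 3.4 is rounded up to 4, and that limits around an observed count are offered as the expectation under a fixed incidence. For the second hypothesis, and for 1:19 itself, the difference is small.

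**The printed ranges are not a decision rule.** The protocol plans a proportion with a binomial interval and formal tests, not classification by range. By likelihood, the second hypothesis overtakes the first from 8 cases whatever ranges are printed. Correcting the third moves its crossover with the second from 51 to 44 cases, so only counts of 44–50 would be assigned differently. This stands and limits the practical effect.

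**Conclusion.** The third benchmark is wrong as written. On the protocol's own inputs it is about 1:23 and 97 cases (78–116), against the stated 1:19 and 118, a 22% overstatement that appears in two sections. The conclusion assumes that the ~1:670 LSCS rate is the intended obstetric spontaneous rate. If another was used, the fault is that it is not stated.

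The intervals are a lesser matter of labelling and of one rounding.

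A reader might go further and infer that the primary analysis or the sample size is compromised. The document does not support that. The sample size comes from expected recruitment, the power statement uses 1:660 and three times that rate, and the estimated proportion and its interval do not depend on the third hypothesis. Expected counts of about 3, 15 and 97 remain far apart. The point is of moderate weight: a prespecified comparator should be right, but the error is unlikely to change which hypothesis the data favour.

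**What to change.** - In sections 5 and 12.2.2, replace ~1:19 with ~1:23. In section 12.2.2, also replace 118 (98–141) with 97 (78–116). Show the derivation, 670 ÷ (19,000/660), and say that the 1:670 input is the LSCS rate from section 4. If a different spontaneous rate was intended, state it with its source and derive the incidence, count and range from it in both sections.
- In section 12.2.2, give the first two benchmarks as 3.4 (0–7) and 14.8 (8–23). Label all three intervals as 95% ranges of the count under the hypothesis.

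This costs wording in two sections and should be done before the 12-month analysis. Data collection, the recruitment target and the planned tests do not change.

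### Section 12.2.2 tests expected counts (4, 15, 118) with Fisher's exact or chi-squared as if they were observed data, which does not match the one-sample binomial test used for sizing and can contradict the section's own confidence interval

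*Protocol*

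**What the plan says.** Protocol 12.2.1 sizes the study at "equivalent to a point estimate of ~2250 included participants over 12 months". The stated aim of the power calculation is to detect an incidence "that is at least three times the incidence described in the overall surgical patient population", with the reference "taken as 0.15% or 1:660", "using an exact binomial test and one-sided" α of 0.05. The printed power is 88%. This is a one-sample test against a fixed value.

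Protocol 12.2.2 opens by saying that the proportion will be given with binomial confidence intervals and compared with established values. It then turns each hypothesis into an expected number of cases:

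- 1:660: "If so, then we expect ~4 patients (binomial 95% CI 1 – 10").
- 1:152: "Then we expect ~15 (95% CI 8 – 25) patients".
- 1:19: 118 patients, with interval 98 to 141.

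The rule for choosing between them follows: "These figures for each of the three possible outcomes will be compared using" Fisher's exact test or chi-squared testing, which is said to give a definitive answer. No significance level or sidedness is given at that point.

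**The concern.** Fisher's exact test compares two rows of observed counts. The protocol prints no cases and denominator for 1:660, and 1:19 is only a derived ratio. The figures that the sentence refers to are expectations at n = 2250. Entering 4/2250 as a second row gives a fixed reference as much sampling error as the study itself.

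Three things are at stake.

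- The test meant to settle the hypotheses is not the test on which the study was sized.
- It can disagree with the confidence-interval comparison in the same section, and nothing says which prevails. Section 12.2.1 makes a possible extension at 12 months depend partly on whether a statistically significant comparison with documented incidences can be made, so the choice of test could affect that decision.
- The counts 4, 15 and 118 match their references only at n = 2250, and 12.2.1 expects that the final number may be lower or higher.

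**Working it through.** **Inputs.** n = 2250; reference p0 = 0.15% or 1/660 = 0.1515%; alternative 3 × p0 = 0.45% to 0.4545%; one-sided α = 0.05 (all from 12.2.1). Expected counts from 12.2.2: 2250/660 = 3.41, printed as 4; 2250/152 = 14.8, printed as 15; 2250/19 = 118.4, printed as 118. Earlier obstetric cohort: 5 of 763 (section 4).

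**The protocol's 88%.** Take the smallest r with P(X ≥ r | n, p0) ≤ 0.05; power is P(X ≥ r | n, 3p0).

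- r = 7: size 0.056 (p0 = 0.15%) or 0.058 (1/660), above 0.05; power 87.8% or 88.4%.
- r = 8: size 0.022 or 0.023; power 79.1% or 80.0%.

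The exact test therefore needs 8 cases and has about 80% power. The printed 88% matches a critical count of 7 or a normal approximation (88.0-88.2%), not the exact test at 0.05. Since 0.023 is also below 0.025, the critical count stays at 8 for a two-sided 5% test, so the comparisons below are like for like.

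**The printed intervals.** Exact (Clopper-Pearson) 95% limits for 4, 15 and 118 observed out of 2250 are 1.09-10.23, 8.41-24.69 and 98.1-140.6 cases. Rounded, these are the printed 1-10, 8-25 and 98-141. The expected counts are already being handled as observations.

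**Power against 4/2250.** For the table [x, 2250 − x; 4, 2246], find the smallest x above 4 with p < 0.05, then P(X ≥ x | 2250, 3/660).

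| Test at 5% | Cases needed | Power at 3/660 |
|---|---|---|
| Fisher, two-sided | 13 | 23.0% |
| Fisher, one-sided | 12 | 32.9% |
| Chi-squared, no correction | 12 | 32.9% |
| Chi-squared, Yates | 14 | 15.2% |
| One-sample exact binomial | 8 | 80.0% |

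With 3.41 rounded to 3 instead, two-sided Fisher needs 12 cases (32.9%) and one-sided Fisher needs 10 (57.1%).

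**If the truth is 1:152.** P(X ≥ 13) = 71.7% with two-sided Fisher, against P(X ≥ 8) = 98.0% with the exact binomial test.

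**Undecided zone.** Two-sided Fisher against 15/2250 rejects on the low side only at 5 or fewer cases (p = 0.041 at 5, 0.078 at 6). Against 4/2250 it rejects from 13 (p = 0.049; 0.076 at 12). Counts of 6 to 12 reject neither. P(6 ≤ X ≤ 12) is 28.0% if 1:152 is true and 71.1% at three times 1:660.

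**Conflict within the section, 10 cases.** Two-sided Fisher against 4/2250: p = 0.18. Exact binomial against 1/660: p = 0.003. Exact 95% interval: 0.21%-0.82%, which excludes 0.1515%.

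**The 1:152 reference.** This rests on a real cohort. The exact 95% interval for 5/763 is 0.21%-1.52%; for 15/2250 it is 0.37%-1.10%. Scaling up to 15/2250 overstates what is known about that rate.

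**The case against.** The strongest reply is that 12.2.2 already contains a valid one-sample comparison: the binomial interval set against established values. It performs well. The exact interval for 8 cases is 0.154%-0.699% and excludes 1:660; for 7 cases it is 0.125%-0.640% and does not. It therefore rejects from 8 cases, with the same 80% power. No count at n = 2250 gives an exact interval containing both 1:660 and 1:152 (at 7 the upper limit, 0.640%, is below 0.658%). A reader might infer that the primary analysis as a whole cannot detect a threefold incidence, or cannot separate the first two hypotheses. The document does not support that, because the interval comparison can do both. What remains is that a later sentence names different tests as the means of deciding, and the two routes can give opposite answers.

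Second, the sentence prints no table. Chi-squared could be read as a one-sample goodness-of-fit test, which also rejects 1:660 from 8 cases (p = 0.013; 0.052 at 7). Fisher's exact test, named first, has no such reading. Fisher against the real counts of a published study would be legitimate, but the sentence points to the expected counts. If it means comparing 4, 15 and 118 with one another, the study's data never enter the test.

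Third, 23% is one variant. That is right: no sidedness is stated in 12.2.2, and the range must be given.

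Fourth, the study is described as descriptive, and test details are often left to an analysis plan. The estimate and interval are indeed untouched. But this protocol has named a method, and it is the wrong one for a fixed reference.

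**Conclusion.** The point holds for the hypothesis-testing sentence in 12.2.2. As written it treats fixed incidences as a second observed cohort of 2250, does not match the sizing test in 12.2.1, and can contradict the interval comparison in its own section.

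At n = 2250 and a true incidence of three times 1:660, power against 4/2250 is about 15-33%, or 33-57% with Fisher if the expected count is rounded to 3. The one-sample exact test or exact interval has 80%. With two-sided Fisher, 28% of studies would leave both of the first two hypotheses standing when 1:152 is true.

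These figures assume exactly 2250 women, a 5% level, and the two-row reading of the sentence. The loss concerns the comparisons with 1:660 and 1:152. The comparison with 118 is not short of power, and the estimated proportion and its interval do not change.

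**What to change.** Replace the sentence in 12.2.2. Compare the observed number of cases with 1:660 and with 1:19 by the one-sample exact binomial test already named in 12.2.1, taking the actual number of women as n, and state the level and sidedness. Specify the binomial interval as exact, so that interval and test agree. If a two-sample test against the earlier obstetric cohort is wanted, use its real data, 5/763. Keep 4, 15 and 118 only as illustrations of what to expect at 2250, and do not enter them in any test.

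While 12.2.1 is open, correct the printed power: the stated exact test gives about 80% (critical count 8), not 88%.

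The cost is one sentence of wording and one corrected figure. No further data are needed.

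### Section 12.2.2 picks among three hypotheses with Fisher's exact or chi-squared tests on expected counts, which are not data; the rule does not match the powered test and cannot be definitive

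*Protocol*

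**What the plan says.** Section 12.2.1 gives a target that is "equivalent to a point estimate of ~2250 included participants over 12 months". It takes the general surgical incidence as a fixed reference, "taken as 0.15% or 1:660", and an alternative of "at least three times the incidence described in the overall surgical patient population". Power is stated for a one-sample comparison with that reference, "using an exact binomial test and one-sided α of 0.05 is 88" per cent.

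Section 12.2.2 first says that the proportion will be given with binomial confidence intervals and set against established values. It then lists three competing hypotheses, each turned into an expected count:

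- 1:660: "If so, then we expect ~4 patients (binomial 95% CI 1 – 10").
- 1:152, from the earlier obstetric study: "Then we expect ~15 (95% CI 8 – 25) patients".
- 1:19, from the ratio of Brice-detected to spontaneous reports: 118 patients, interval 98 to 141.

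These figures are then to be compared by Fisher's exact or chi-squared testing "to yield a definitive answer as to which is the most likely hypothesis of the three". No sidedness, comparator denominator or decision rule is given.

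Section 4 shows what lies behind 1:152: "A total 763 of 1095 obstetric patients were provided Brice questionnaires", with five positive cases. It describes the confidence intervals of that study as wide.

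**The concern.** Fisher's exact test and the usual two-group chi-squared test compare two observed samples. The three figures are a fixed rate multiplied by the planned sample size, so there is no second sample.

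The sentence can be read in two ways. On the literal reading, the expected counts are compared with each other and the result is known before the study starts. On the more generous reading, the observed count is compared with each figure as if that figure were a second group of 2250. The second reading gives 1:660 a sampling error that the power statement does not give it. It also gives 1:152 the precision of 15/2250, when it rests on 5/763.

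Either way, the test named for the verdict is not the test the study was powered on. Failing to reject a hypothesis also does not make it the most likely one. Choosing among the three rates is the research question in section 5. Section 12.2.1 further ties a possible extension of the study partly to whether a significant comparison with earlier incidences can be made.

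**Working it through.** **Inputs.** n = 2250; reference 1/660 (0.1515%) or 0.15%; alternative three times the reference (0.45% to 0.4545%); hypotheses 1/660, 1/152 and 1/19 (12.2.1 and 12.2.2); earlier obstetric study 5/763 (section 4).

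**1. The plan's own figures.** Expected counts are 2250/660 = 3.4 (printed as about 4), 2250/152 = 14.8 and 2250/19 = 118.4. Exact (Clopper-Pearson) limits, expressed as counts out of 2250, are 1.1–10.2 for 4, 8.4–24.7 for 15 and 98.1–140.6 for 118. These match the printed ranges.

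For the stated power, find the smallest r with P(X ≥ r | n, p0) ≤ 0.05, then compute P(X ≥ r | n, 3p0):

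| Cut-off r | Actual α (p0 = 0.15%; 1/660) | Power at 3p0 |
|---|---|---|
| 7 | 0.056; 0.058 | 87.8%; 88.4% |
| 8 | 0.022; 0.023 | 79.1%; 80.0% |

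A cut-off of 7 exceeds 0.05, so the exact test rejects from 8 cases and has 79–80% power. The stated 88% matches a one-sided normal approximation (88.0–88.2%). That is a separate matter, but 79–80% is the right baseline here. With the same cut-off of 8, power at 1:152 is 98%.

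**2. Literal reading: figures compared with each other.** Fisher on 4/2250 v 15/2250 gives p = 0.019; 15 v 118 gives p < 10⁻²⁰. These values are the same whatever the study observes.

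**3. Observed count against a figure treated as a group of 2250.** The cut-off is the smallest x for which Fisher's test of x/2250 against e/2250 has p ≤ 0.05. Power is P(X ≥ cut-off), with the expected 3.4 rounded to 3 or 4:

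| e | Sidedness | Rejects from | Power at 3 × 1/660 | Power at 1/152 |
|---|---|---|---|---|
| 3 | one-sided | 10 | 57% | 92% |
| 3 | two-sided | 12 | 33% | 80% |
| 4 | one-sided | 12 | 33% | 80% |
| 4 | two-sided | 13 | 23% | 72% |
| One-sample exact binomial | one-sided | 8 | 80% | 98% |

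The figures depend on the test. Two-sample chi-squared gives about 15–69% at 3 × 1/660, depending on continuity correction and sidedness. A one-sample goodness-of-fit chi-squared gives 80–88%, so it loses little or nothing.

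**4. Can it decide?** Two-sided Fisher does not reject 4/2250 for counts up to 12, and does not reject 15/2250 for counts 6 to 28. Counts 6–12 therefore reject neither. P(6 ≤ X ≤ 12) is 28% if the truth is 1/152 and 71% if it is 3 × 1/660. Yet within that zone the data can discriminate. The binomial likelihood ratio of 1:152 to 1:660 is 1.4 at 8 cases and 27 at 10 cases.

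**5. The precision of 1:152.** The exact 95% interval for 5/763 is about 1:469 to 1:66. For 15/2250 it is about 1:268 to 1:91, which is clearly narrower. A two-sided Fisher test of the observed count against the real 5/763 does not reject for any count from 4 to 36.

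**6. The interval already planned.** With n = 2250 the exact 95% interval contains 1:660 for counts 0–7, 1:152 for 8–23 and 1:19 for 98–140. The sets do not overlap, and any other count excludes all three.

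**The case against.** The strongest reply is that 12.2.2 already opens with a sound analysis: a binomial confidence interval set against established values, in a study that 12.2.1 calls descriptive. As step 6 shows, the exact form of that interval separates the three rates and allows for none of them. This stands, and it is why the point is not graded higher. A reader might infer that the primary result as a whole would rest on an invalid, badly underpowered test. The document does not support that, because the proportion and its interval would be reported in any case.

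A reader might also take 23–57% as the power to tell the three hypotheses apart. It is not. It applies to Fisher's test only, at three times 1:660, which is the alternative in the power statement and not one of the three hypotheses. For 1:660 against 1:152 the corresponding range is 72–92%, and 1:19 is so far away that it is never in doubt.

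Nor can it be said that a true rate between the benchmarks gets no usable result: rejecting all three is informative, although the sentence makes no provision for it.

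Finally, the group of 2250 is an assumption, since the protocol gives no comparator denominator. "Chi-squared" could mean a one-sample goodness-of-fit test, and a two-sample test is legitimate against the earlier study's real data. Both points stand. They narrow the power loss, but the text specifies neither reading, and neither would rank three hypotheses definitively.

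**Conclusion.** The sentence is wrong as written and should be fixed. Expected counts are not samples, the test named for the verdict differs from the one-sample exact binomial test used for power, and non-rejection cannot identify the most likely of three hypotheses.

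If each figure is treated as a group of 2250 and Fisher's test is used against 3 or 4 cases, power falls from 98% to 72–92% at 1:152 and from 79–80% to 23–57% at three times 1:660. With two-sided Fisher against 4 and 15, there is a 28% chance of no verdict between 1:660 and 1:152 even when 1:152 is exactly true. These sizes assume n = 2250 and the two-sample reading; chi-squared variants differ, and a one-sample goodness-of-fit test would lose little. The planned confidence interval contains the damage, so the fault lies in the decision rule and its claim, not in the estimate.

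**What to change.** In 12.2.2, replace the Fisher/chi-squared sentence with the following:

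- Report the exact binomial 95% confidence interval as the basis of comparison with all three rates.
- Test the observed count against the fixed values 1:660 and 1:19 with one-sample exact binomial tests, with sidedness and α stated and, for 1:660, in line with 12.2.1.
- Rank the three hypotheses by likelihood ratio, stating that each rate is taken as fixed. Conclude that none of the three holds when the exact 95% interval excludes them all.
- Keep a two-sample exact test only for comparison with the earlier obstetric study's actual 5/763, and note its low precision (no rejection for counts 4 to 36).
- Delete the promise of a definitive answer.

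The cost is a few sentences. No new data, sample size change or extra follow-up is needed.
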